Mental health treatment adherence. We will ask respondents if they have been prescribed medication for depression and about difficulties taking medication(s) regularly. Questions will adapted from Katon's Team Care Intervention.¹¹²

Co-variates

Sociodemographics. We will draw the following measures from the NCI's HINTS survey;¹²⁷ race, ethnicity, age, education, language spoken, foreign born, years in the U.S., marital status, parental status, household composition, employment status, insurance status, education, and income.

Past history of cancer. We will use questions from the NCI's HINTS survey¹²⁷ to determine whether the respondent has ever been diagnosed with cancer, and if so, what type of cancer and when. We will also ask women if they have had a hysterectomy and confirm through the electronic medical record whether this was a full hysterectomy that included removal of the cervix.

Family history of cancer. Questions about family history of cancer will come from the NCI's HINTS survey.¹²⁷

Chronic medical conditions and obesity.

Information about the respondents' chronic medical conditions as well as weight, height, and body mass index as an indicator of obesity will be drawn from the electronic medical records. **Anxiety (GAD-7).** The GAD (Generalized Anxiety Disorder)-7 is based on diagnostic criteria in the DSM-IV and measures probably anxiety disorder and severity of anxiety symptoms. Patients are asked to rate how often they have been bothered by 7 problems in the last 2 weeks on a 4-point (0-4) scale ("not at all" to "nearly every day"). At a cut point of 10, sensitivity is 89% and specificity is 82%. In multiple diverse primary care samples of over 2000 patients, the measure demonstrated excellent validity as well as high internal reliability and test-retest reliability (Cronbach's alpha=0.92 and intraclass correlation=0.83, resp.).^{167,168} Factorial analysis demonstrated that the GAD-7 measures anxiety as distinct from depression.¹⁶⁸ A Spanish-language version has also demonstrated very good specificity and sensitivity as well as excellent reliability and validity.¹⁶⁹

G. STUDY SUBJECTS

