We will recruit 800 women to the study. To be eligible for the study, women must be patients at one of the six participating Bronx CHCs. They must also be between 50 and 64 years of age, speak English or Spanish, reside in the Bronx, screen positive for depression based on the PHQ-9 (≥ 8) at time of recruitment, and be out-of-adherence with current U.S. Preventive Services Task Force cancer screening guidelines for breast, cervical, and/or colorectal cancer screening. Women will be considered out of adherence if they have not received a Pap test without HPV in the past three years or a Pap test with HPV in the past five years, a mammogram in the past two years, and/or one of the following forms of colorectal screening: FOBT (or FIT) within the past year, flexible sigmoidoscopy in the past five years, or colonoscopy in the past 10 years. A woman who has had total hysterectomy is considered up-to-date for cervical cancer screening after the date on which the hysterectomy was performed.⁷⁶ We aim to be as inclusive as possible in this study. However, to maximize feasibility and in keeping with prior collaborative care research^{99,112}, we will exclude women who report the following when screened: terminal illness, current pregnancy (albeit unlikely in this age range), substance use, decisionally impaired or suicidal thoughts. We will exclude prisoners. Data received from the six health center sites support the availability of potential study participants and demonstrate the need for a study such as this one. In 2011, across the study sites, mammography rates for women 50-64 years of age were 56%, 57% and 64%; Pap testing rates were 62%, 50% and 53%. All of these rates fell substantially below the New York City target of 85% or greater. For colon cancer screening, rates in 2011 were 24%, 52%, and 27%, also much lower than the New York City target of 60% or greater. Additionally, depression rates for women of this age range in 2011 were 35% (including dysthymia), 21%, and 21%, which is consistent with the literature.

H. RECRUITMENT OF SUBJECTS

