Colonoscopy) were compared separately between the two intervention arms using a chi square test comparing two independent binomial proportions (Aim 1). Next, logistic regression was used to control for potential confounders, including the factors discussed that were identified as being unevenly distributed between the CCI and PCM intervention arms at baseline. To account for possible differences by site, site indicators were included in the model as a fixed effect to examine if there were potential confounders; if they were not found to be confounders, they were removed from the model. A combined ordinal cancer screening outcome, calculated as number of up to date cancer screening tests (which vary from 0 to 3) was analyzed using the proportional odds model (PROC GENMOD in SAS). Other key patient-reported outcomes, including changes in depression, self-efficacy, stigma, satisfaction with cancer screening decision and satisfaction with care, and quality of life, were also compared between the two intervention arms (Aim 2). For continuous outcomes, a two-sample t-test was used to examine the difference between the two arms, and a linear regression model was used to control for potential confounders; for categorical outcomes, a chi-square test was used to examine the difference between the two arms and a logistic regression (for binary outcome) or a multinomial logistic regression (for a categorical outcome with more than two levels) was also used to control for potential confounders.

Multivariate analyses testing for moderators and mediators

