Heterogeneity of Treatment Effects (HTE) Analysis

A potential problem in intervention studies is heterogeneity within the participant population. To examine whether the effectiveness of intervention varies according to patient characteristics, here we focused on BMI and primary language as previous evidence supported that these two characteristics affected the likelihood of being up to date with cancer screening. In addition, because women who were up to date at baseline may be very different from women who were not up to date at baseline, we examined the subset of women who were not up to date for each specific cancer screening and examined if the intervention improved their up to date screening status.

Sample size/Power Calculation

The primary aim of the study was to compare the effectiveness of the Collaborative Care Intervention (CCI) versus Prevention Care Management (PCM) to increase participation in screenings for cervical cancer, breast cancer and colon cancer among women with depression. Women were equally randomized to the two intervention arms. With 356 women in each arm, the study had about 80% power to detect a minimum 10% difference between two arms in cancer screening participation with a two-sided type I error rate of 5%, under various assumptions of screening rate for the PCM (control) group. This 10% difference is considered the smallest difference of interest, based on previous studies comparing the PCM to Usual Care.^{1, 2,3} Therefore, with 356 women with complete data per intervention arm (n=712) our study had sufficient power to detect a clinically meaningful difference between the two intervention arms.

Multiple Comparisons

We evaluated three separate screening outcomes (for cervical cancer, breast cancer and colorectal cancer) so that multiple hypothesis testing would be involved. However, the relative importance of factors contributing to participation in each screening test varied between tests, and we were interested in comparing the two intervention arms for each test separately, as well as globally for all three tests. We also examined a summary of cancer

screening outcome across three types of cancers by comparing the total number of up to date cancer screenings at the follow-up between the two treatment arms, using a regression model for ordinal outcome. Since these statistical tests were hypothesis-driven rather than exploratory, we did not think multiple comparison adjustment for type I error rate was necessary.

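### Women with total hysterectomy stay in the main cervical comparison with a fixed outcome and no stated scoring rule, which attenuates the cervical risk difference and costs power

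*Protocol*

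**What the plan says.** Protocol section G (Study Subjects) sets out which women are overdue for screening and adds that "A woman who has had total hysterectomy is considered up-to-date for cervical cancer screening" once the operation has taken place. Entry requires only one overdue test among the three, so a woman without a cervix is eligible if she is overdue for a mammogram or for colorectal screening.

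The SAP (Intention to treat analysis) compares completion of each test between arms with a chi-square test, naming the Pap test as the cervical measure. It then defines a combined ordinal outcome, "calculated as number of up to date cancer screening tests (which vary from 0 to 3"), analysed with a proportional odds model. The protocol's self-report item (section F, Primary Outcomes) asks yes or no about a Pap test in the past three years. None of these places says what happens to a woman who has no cervix.

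The information needed is already collected. Under Co-variates in section F the protocol states: "We will also ask women if they have had a hysterectomy and confirm through the electronic medical record", to establish whether the cervix was removed.

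The SAP's section on heterogeneity of treatment effects also describes a per-test analysis restricted to women not up to date for that test at baseline.

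**The concern.** A woman whose cervix was removed before enrolment cannot have, miss or respond to cervical screening. Whatever code she receives is the same in both arms and cannot change. Keeping her in the cervical denominator adds a block of women in whom the treatment difference is zero by construction. The estimated risk difference then describes a mixture of women who could respond and women who could not.

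The wording also points two ways. Counting up-to-date tests, read with the eligibility rule, gives her a success. Completion of a Pap test, or a yes/no item about a recent Pap, read literally gives her a failure. Chart review, self-report and the combined count could therefore score the same woman differently. At stake are the size and precision of one of the three main screening comparisons, and the meaning of the reported cervical screening rate.

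**Working it through.** **Inputs.** From the SAP (Sample size/Power Calculation): "the study had about 80% power to detect a minimum 10% difference between two arms", "two-sided type I error rate of 5" per cent, and "with 356 women with complete data per intervention arm (n=712"). The control rate is not given as a number; the SAP says "under various assumptions of screening rate for the PCM (control) group". Protocol section G gives 2011 site figures as a guide: "Pap testing rates were 62%, 50% and 53" per cent. The hysterectomy share h is not given; 10%, 20% and 30% are assumptions.

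**Step 1: reproduce the plan's figure.** Pooled two-proportion test, 1:1, no continuity correction:

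n per arm = [1.960·√(2p̄(1−p̄)) + 0.842·√(p₁(1−p₁)+p₂(1−p₂))]² / d²

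With p₁ = 0.60, p₂ = 0.70, p̄ = 0.65, d = 0.10: (1.960×0.6745 + 0.842×0.6708)² / 0.01 = 355.9, so 356 per arm and 80.0% power. By symmetry 30% versus 40% gives the same. At the site Pap rates, power for 10 points is 76.6% (50%), 77.3% (53%) and 81.1% (62%). The stated 80% is reproduced.

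**Step 2: bring in h.** Let p be the rate among women with a cervix.

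- Scored as successes: arm rate = h + (1−h)p
- Scored as failures: arm rate = (1−h)p
- Difference under either scoring = (1−h) × 10 points, that is 9, 8 or 7 points
- Excluded: rate p, difference 10 points, n per arm = 356(1−h), about 320, 285 or 249

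**Step 3: power.** Power = Φ{[d√n − 1.960√(2p̄(1−p̄))] / √(p₁(1−p₁)+p₂(1−p₂))}.

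Worked at h = 20%:

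- Successes, 68% vs 76%, n = 356: (1.509 − 1.245)/0.632 = 0.419, power 66.2%
- Failures, 48% vs 56%, n = 356: (1.509 − 1.385)/0.704 = 0.177, power 57.0%
- Excluded, 60% vs 70%, n = 285: (1.688 − 1.322)/0.671 = 0.546, power 70.7%

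| h | Successes | Failures | Excluded |
|---|---|---|---|
| 0% | 80.0% | 80.0% | 80.0% |
| 10% | 73.5% | 68.4% | 75.7% |
| 20% | 66.2% | 57.0% | 70.7% |
| 30% | 58.4% | 46.6% | 64.9% |

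**Step 4: separate the avoidable loss.** Excluded minus successes is 2.2, 4.5 and 6.5 points. Excluded minus failures is 7.3, 13.7 and 18.3 points. The remaining fall from 80.0% to the excluded column (4.3, 9.3 and 15.1 points) comes from having fewer women at risk, and no scoring rule recovers it.

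**Step 5: vary the control rate.** At 50% versus 60%, power at h = 10/20/30% is 68.7/60.4/52.0% as successes, 67.1/57.6/48.4% as failures and 72.1/67.0/61.2% excluded. At 45% versus 55%, a rate below the site figures, it is 67.6/58.7/49.9% under either scoring and 71.7/66.6/60.8% excluded. At 30% versus 40% the success and failure columns of the table change places. Exclusion has the highest power in every case examined.

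**Step 6: the 0–3 count.** Assume independent tests, 60% control rates, a uniform 5-point effect and scoring as successes. The mean difference is 0.05 × (2 + (1−h)): 0.150 at h = 0, 0.145 at 10% and 0.135 at 30%. Approximate power (Wilcoxon, standing in for the proportional odds test) is 66.1%, 63.8% and 59.5%. With a uniform 10-point effect it stays above 99%.

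**The case against.** A reader might infer that these women are automatic successes and that reported Pap completion is therefore overstated in both arms. The documents do not support that. The rule sits in eligibility text, and the separate cervical endpoint could equally score such a woman as not screened, which would understate the rate. What can be said is that the scoring is undefined and the outcome is fixed either way.

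The strongest defence is the SAP's own analysis of women not up to date at baseline for each test. If the eligibility rule is applied, it drops every woman with a prior hysterectomy and gives an undiluted cervical comparison. This stands in part: that analysis is listed under heterogeneity of treatment effects, not as the main intention-to-treat comparison, and it does not cover the count.

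A logistic model with a hysterectomy indicator would also remove the dilution from the treatment coefficient, because a stratum with a constant outcome carries no information about it. That is correct, but the SAP names no such indicator, and the unadjusted chi-square comes first.

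The 10-point target may already be on a scale that includes these women. The SAP bases it partly on an earlier telephone care management trial, and the protocol cites the same trial for the hysterectomy rule. This cannot be settled from the documents. It limits any claim that the study is underpowered against its own target, but not the comparison between including and excluding.

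Finally, women already up to date by an actual test cause similar dilution. That is true, but they can fall overdue during follow-up, whereas a woman without a cervix cannot change status.

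**Conclusion.** The point holds as an undefined scoring rule combined with a denominator that includes women who cannot respond. The cervical risk difference is multiplied by (1−h) under either scoring. At 60% versus 70% and h of 10% to 30%, exclusion would recover 2.2 to 6.5 power points relative to scoring as successes, and 7.3 to 18.3 relative to scoring as failures. These sizes rest on an assumed h and an assumed control rate, and on taking the 10-point effect to apply to women with a cervix.

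A reader might also infer a biased comparison between arms. That does not follow: hysterectomy before enrolment is balanced by randomisation in expectation, so the result is attenuation and lost power, with no threat to the type I error rate. The effect on the 0–3 count is small because only one of its three components is affected. This is a worthwhile, inexpensive improvement and not a flaw that invalidates the trial.

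**What to change.** Keep the eligibility rule as it is. In the SAP:

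- Make women without a chart-confirmed total hysterectomy at baseline the denominator of the main cervical analysis. Use baseline status only, so that the exclusion cannot depend on anything after randomisation.
- State one scoring rule for hysterectomy that applies alike to the chart, self-report and count outcomes, including an operation during follow-up.
- For the combined outcome, either include a separate hysterectomy indicator, not merged with women up to date by an actual test, or analyse tests completed among tests applicable.
- Report the number of women with total hysterectomy by arm.

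The cost is a few sentences and no new data, since hysterectomy status is already asked about and checked in the record. As the SAP describes the analyses in the past tense, the change can be presented as a labelled re-analysis beside the original results. The downside is a smaller cervical denominator: about 320, 285 or 249 per arm at h = 10%, 20% or 30%, from 356.

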Statistical Analysis Plan

Collaborative Care to Reduce Depression and Increase Cancer Screening among Low-Income Urban Women

NCT Number: 02273206

Document Date: July 30, 2017

**Collaborative Care to Reduce Depression and Increase Cancer
Screening among Low-Income Urban Women – Prevention Care Manager 3 Project**

Statistical Analysis Plan

Overview

The primary analysis was based upon the intention-to-treat (ITT) approach, with data from each participant analyzed as per initial assignment to one of the two intervention arms. Our analysis proceeded in several steps: 1) data checking to identify and resolve the reasons for missing values, inconsistencies, and out-of-range values; 2) descriptive analyses of the baseline characteristics of the two intervention arms; 3) formal comparison of participation in screening tests and changes in depression between the CCI intervention and PCM controls arms, intention-to-treat analyses, per protocol analyses, and analyses that accounted for missing data; and 4) multivariate analyses testing for moderators and mediators.

Data checking and descriptive analysis

Data analysis was preceded by intensive data checking to identify and resolve the reasons for missing values, inconsistencies, and out-of-range values. Summary statistics describing the baseline characteristics of each intervention arm are presented, including age, primary language, marital status, health insurance, smoking status, body mass index, medical history, family history and comorbid conditions, etc. Continuous variables were summarized using means and standard deviations, while categorical variables were summarized using proportions with cut points made for median or quartiles as appropriate. A comparison of the distribution of baseline characteristics was made between the two intervention arms. There were no differences between the two groups with respect to their distribution by baseline characteristics. In addition to the baseline characteristics, we tabulated the study endpoints of interest, the extent of dropouts, and protocol violations for each intervention arm separately.

Intention to treat (ITT) analysis

Data from each study subject were analyzed as per initial assignment to the intervention arm. First, completion of cervical cancer screening (Pap test), breast cancer screening (mammogram), and colon cancer screening (HFOBT/FIT, Barium Enema, Sigmoidoscopy or

Colonoscopy) were compared separately between the two intervention arms using a chi square test comparing two independent binomial proportions (Aim 1). Next, logistic regression was used to control for potential confounders, including the factors discussed that were identified as being unevenly distributed between the CCI and PCM intervention arms at baseline. To account for possible differences by site, site indicators were included in the model as a fixed effect to examine if there were potential confounders; if they were not found to be confounders, they were removed from the model. A combined ordinal cancer screening outcome, calculated as number of up to date cancer screening tests (which vary from 0 to 3) was analyzed using the proportional odds model (PROC GENMOD in SAS). Other key patient-reported outcomes, including changes in depression, self-efficacy, stigma, satisfaction with cancer screening decision and satisfaction with care, and quality of life, were also compared between the two intervention arms (Aim 2). For continuous outcomes, a two-sample t-test was used to examine the difference between the two arms, and a linear regression model was used to control for potential confounders; for categorical outcomes, a chi-square test was used to examine the difference between the two arms and a logistic regression (for binary outcome) or a multinomial logistic regression (for a categorical outcome with more than two levels) was also used to control for potential confounders.

Multivariate analyses testing for moderators and mediators

To determine whether reducing depression increases the likelihood that low-income women will receive age-appropriate cancer screening (Aim 3), we included improvement in depression (as well as depression remission in a separate model) in the logistic regression models to examine its association with cancer screenings, and also to examine if the difference between the two intervention arms was modified by change in depression; we examined the interaction between improvement in depression and treatment (as well as depression remission and treatment). To determine whether the effectiveness of the CCI intervention varies according to patient characteristics, such as language spoken and, obesity, etc. (Aim 4), we examined each of these variables as possible effect modifiers. However, it is understood that the statistical power for testing an interaction term may be limited in this study; consequently, this aim was treated as exploratory and the results of this study will be used to design a future, more definitive study with interventions identified and targeted to address issues associated with specific subgroups who may experience reduced benefit from the intervention.

Missing Data

Missing data are a common problem in longitudinal studies. In the context of the present study, missing data will occur when, for example, not all the screening outcomes are reported for a given participant, or some of the co-variables (e.g., body mass index) are missing. For the initial approach in the primary analysis of the study, study participants with missing values on either the outcomes or the co-variables were first removed from the study for the evaluation of intervention effects. However, this approach required the assumption of missing completely at random to be true. A violation of this assumption may lead to bias in the estimate of the intervention effect. We first examined the level of missing data by each outcome and each co-variate in the model. If the rate of missing data is small (<5%), the chance that it will bias the result is very low; however, if the rate of missing data is moderate (>10%), sensitivity analysis was used to examine the robustness of the result. For example, if one variable has a moderate level of missing, we conducted a sensitivity analysis which compared those participants with the remaining participants and also included those participants in the analyses by adding a separate missing category.

Heterogeneity of Treatment Effects (HTE) Analysis

A potential problem in intervention studies is heterogeneity within the participant population. To examine whether the effectiveness of intervention varies according to patient characteristics, here we focused on BMI and primary language as previous evidence supported that these two characteristics affected the likelihood of being up to date with cancer screening. In addition, because women who were up to date at baseline may be very different from women who were not up to date at baseline, we examined the subset of women who were not up to date for each specific cancer screening and examined if the intervention improved their up to date screening status.

Sample size/Power Calculation

The primary aim of the study was to compare the effectiveness of the Collaborative Care Intervention (CCI) versus Prevention Care Management (PCM) to increase participation in screenings for cervical cancer, breast cancer and colon cancer among women with depression. Women were equally randomized to the two intervention arms. With 356 women in each arm, the study had about 80% power to detect a minimum 10% difference between two arms in cancer screening participation with a two-sided type I error rate of 5%, under various assumptions of screening rate for the PCM (control) group. This 10% difference is considered the smallest difference of interest, based on previous studies comparing the PCM to Usual Care.^{1, 2,3} Therefore, with 356 women with complete data per intervention arm (n=712) our study had sufficient power to detect a clinically meaningful difference between the two intervention arms.

Multiple Comparisons

We evaluated three separate screening outcomes (for cervical cancer, breast cancer and colorectal cancer) so that multiple hypothesis testing would be involved. However, the relative importance of factors contributing to participation in each screening test varied between tests, and we were interested in comparing the two intervention arms for each test separately, as well as globally for all three tests. We also examined a summary of cancer

screening outcome across three types of cancers by comparing the total number of up to date cancer screenings at the follow-up between the two treatment arms, using a regression model for ordinal outcome. Since these statistical tests were hypothesis-driven rather than exploratory, we did not think multiple comparison adjustment for type I error rate was necessary.

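### The per-test chi-square ignores whether a woman was already up to date for that test at entry; it stays valid but gives up precision, by an amount that depends on how the outcome is defined

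*SAP*

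**What the plan says.** Protocol section G requires a woman to "be out-of-adherence with current U.S. Preventive Services Task Force cancer screening guidelines for breast, cervical, and/or colorectal cancer screening". One overdue test is enough; she may be up to date for the other two.

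The SAP section on intention-to-treat analysis opens the outcome list with "First, completion of cervical cancer screening (Pap test), breast cancer screening (mammogram" and then colorectal tests. These outcomes "were compared separately between the two intervention arms using a chi square test comparing two independent binomial proportions". Logistic regression for possible confounders follows, "including the factors discussed that were identified as being unevenly distributed between the CCI and PCM intervention arms at baseline". That list is open, but imbalance is the only criterion it names, and the SAP section on data checking reports: "There were no differences between the two groups with respect to their distribution by baseline characteristics".

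Baseline screening status is used once, under heterogeneity of treatment effects, where "we examined the subset of women who were not up to date for each specific cancer screening". Under Multiple Comparisons the 0-to-3 summary is analysed by "comparing the total number of up to date cancer screenings at the follow-up between the two treatment arms", with no mention of the number at entry.

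The covariate is available. Protocol section F lists self-reported screening as an outcome measure, section C puts self-report measures in all three interviews, and randomisation follows the baseline interview.

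**The concern.** If the outcome is being up to date at follow-up, a woman's status at entry is likely to be one of its strongest predictors. A plain two-proportion test leaves that variation in the error term. A rule that adjusts only for imbalanced factors misses the point of such a covariate: the gain comes from its link with the outcome, not from chance imbalance.

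There is a second, separate effect. Readiness is assessed only for tests a woman is overdue for (Protocol section C, Initial phone contact). This suggests, without proving, that any effect on a test falls mainly in women overdue for it. If so, the all-women difference is smaller than the difference in overdue women. Adjustment does not cure that.

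The stake is how a null result is read. Protocol section B says that failing to reject the null, taken as PCM alone doing as well as CCI, would itself matter for service delivery. A wider interval supports that reading less.

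**Working it through.** **The plan's own figure.** n per arm = [1.96√(2p̄(1−p̄)) + 0.842√(p₁(1−p₁)+p₂(1−p₂))]² / (p₂−p₁)². For 30% vs 40%, or 60% vs 70%, this gives 355.9, so 356 per arm and 80.0% power, as the SAP states. At 45% vs 55% power is 76.2% and 392 per arm are needed.

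**Shares already up to date (assumed).** Protocol section G gives 2011 rates at three sites. The means are mammogram 0.590, Pap 0.550 and colorectal 0.343. Assuming independence, all three are current with probability 0.590 × 0.550 × 0.343 = 0.111, and such women cannot enter. Share up to date given entry = (pᵢ − 0.111)/(1 − 0.111) = 54%, 49%, 26%. Each site's own rates give 50–60%, 41–59% and 17–44%.

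**Base case (assumed).** Outcome up to date at follow-up; overdue women 35% (PCM) vs 45% (CCI); 90% of women current at entry stay current in both arms. For mammogram:

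- PCM 0.539×0.90 + 0.461×0.35 = 0.646; CCI 0.539×0.90 + 0.461×0.45 = 0.692; difference 4.6 points (Pap 5.1, colorectal 7.4).
- Plain SE = √[(0.646×0.354 + 0.692×0.308)/356] = 3.5 points.
- Stratified SE = √[(0.539×2×0.90×0.10 + 0.461×(0.35×0.65 + 0.45×0.55))/356] = 3.0 points.
- Power ≈ Φ(difference/SE − 1.96): 26% plain, 34% stratified.
- Variance explained = s(1−s)(u−o)²/[p(1−p)], with arms pooled: 0.539×0.461×(0.90−0.40)²/(0.669×0.331) = 28%. Equivalent size 356/(1−0.281) = 495 per arm.

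For Pap and colorectal the SEs fall from 3.6 to 3.0 and from 3.7 to 3.3 points, equivalent to about 490 and 441 women per arm.

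**Range.** Power in % for mammogram/Pap/colorectal, from 60,000 simulated trials per case. The closed form agrees to within about 1 point.

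| Women up to date at entry | Plain to stratified |
|---|---|
| *Outcome: up to date at follow-up* | |
| 90% stay, both arms (base) | 26/29/50 to 34/38/59 |
| 90% vs 94% stay | gain 11–15 |
| 80% vs 90% stay (10 points in everyone) | 80/79/76 to 89/88/83 |
| 80% stay, both arms | gain 4–6 |
| 1/2, 1/3, 1/5 fall due; no response to CCI | 23/29/50 to 25/32/58 |
| The same fall due and respond | 51/45/56 to 54/52/65 |
| 90% stay; overdue women carry 10 points overall | 83/82/77 to 91/90/84 |
| *Outcome: tested during follow-up* | |
| None tested | gain 7–10 |
| 20% tested | gain about 1 |
| 35% tested | gain 0.0–0.2 |

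With correlated tests (latent correlation 0.5; shares 47%, 42%, 15%) the base case is 31/35/61 to 40/45/68.

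**Other planned analyses.** In the base case the overdue subset has 46/49/65%. The 0-to-3 summary has 80%, or 87% when stratified by the seven possible baseline patterns (6,000 trials); if women fall due and do not respond, 76% and 80%.

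**Validity.** Null rejection was 4.5–5.2% throughout. The plain chi-square is sound.

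**The case against.** - **The chi-square may not be the sole primary analysis.** The SAP lists it first and the regression next without ranking them, and its Missing Data section speaks of covariates in the primary analysis. The covariate list is open. This stands: baseline status is unspecified, not excluded.
- **The SAP's overdue subset does better than the proposed fix in the base case**, 46/49/65% against 34/38/59%. This also stands. But it estimates the effect in a different population and does not sharpen the all-women estimate. When everyone gains 10 points, the stratified test is the stronger.
- **The base case is favourable.** If 1/2, 1/3 and 1/5 of current women fall due within a year, 90% staying current means that 80%, 70% and 50% of them are retested (for example 1 − 0.10/0.50 = 0.80), against 35–45% of overdue women. Without that, the mammogram gain is about 2 points and the Pap gain about 3; colorectal keeps about 8.
- **Low base-case power is mostly dilution.** The overall differences of 4.6 to 7.4 points are below 10 points, of which the SAP says "This 10% difference is considered the smallest difference of interest". Correct: 26/29/50% should not be read as the cost of omitting the covariate.
- **The reading of a null result may not change.** For mammogram the 95% half-width is 1.96×3.52 = 6.9 points plain and 1.96×2.98 = 5.8 stratified. With an estimate near zero, both exclude 10 points. They differ only for estimates between 10 − 6.9 = 3.1 and 10 − 5.8 = 4.2. The benefit is real but modest.
- **The baseline shares are fragile.** They come from three sites in 2011 and from all women aged 50–64, whereas six sites enrol women with depression.

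**Conclusion.** The concern holds. The per-test comparison does not use baseline status for the test, and nothing in the SAP requires adjusting for it. There is no bias and no inflation of Type I error. The cost is precision: about 8 to 10 points of power in the base case, 0 to 15 across the assumptions tried, and almost nothing if the outcome is testing during follow-up and current women are tested about as often as overdue women. The SAP's wording for the summary outcome points to up-to-date status, where the gain is larger. Every stratum rate is an assumption, because the documents give neither entrants' baseline status nor follow-up rates. The overdue subset and the 0-to-3 summary already reduce the concern. It is worth fixing because the remedy is nearly free, not because the planned test is wrong.

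**What to change.** 1. For each test, add an all-women analysis stratified by, or adjusted for, baseline up-to-date status for that test, whatever the observed balance. Take baseline status from the same source and definition as the outcome. A Mantel-Haenszel risk difference keeps the SAP's 10-point scale; logistic adjustment would give a conditional odds ratio. Adjust the 0-to-3 summary for baseline status as well.
2. Report these beside the stated chi-square with the date they were added. The SAP is written in the past tense, so they can be the main analysis only if fixed before anyone saw outcome data by arm.
3. Report the share up to date at baseline for each test by arm. Show the overdue-subset result next to the all-women result before concluding that PCM alone does as well.

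The cost is a minor extra analysis on data already collected, which may gain almost nothing under one reading of the outcome.

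A separate item, which adds no weight to this point: state whether completion means up to date at follow-up or tested during follow-up. Also reconcile barium enema (in the SAP's colorectal list, absent from Protocol sections F and G) and the Pap/HPV look-back (section G against the self-report item in section F).
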